# **Population:**

This study will use the US-based Optum's Electronic Health Record (EHR) data, with supplemental linkage to Optum's Integrated Claims-Clinical adjudicated claims dataset for those patients in the EHR who also have claims data available. For a subset of patients in the EHR, patient electronic clinical notes exist which will allow manual clinician review at Optum to confirm myocarditis cases based on available data that align with the Brighton Collaboration criteria. The proposed study period is 01 January 2010 to most recent available at the time of start of data collection (31 March 2023)), to allow sufficient baseline time to examine risk factors for patients with myocarditis in each of the three cohorts, with index dates of 2016-later.

Among the overall Optum EHR study population of all ages, the following mutually exclusive cohorts and index dates will be defined to address the study objectives:

- Cohort 1 Post-mRNA COVID-19 vaccination myocarditis cohort: first date of a
  myocarditis diagnosis code within 21 days after vaccination from 11 December 2020 to most
  recent data available, allowing for at least 30 days pre or post index for medical notes to
  confirm diagnosis through end of study period.
- Cohort 2 Post-SARS-CoV-2 infection myocarditis: first date of a myocarditis diagnosis
  code within 8 weeks after a positive SARS-Cov-2 test from 01 January 2020 to most recent
  data available, allowing for at least 30 days pre or post index for medical notes to confirm
  diagnosis through end of study period.
- Cohort 3 Pre-COVID myocarditis: most recent date of a myocarditis diagnosis from 01 January 2016 to 01 November 2019, allowing for at least 30 days pre or post index for medical notes to confirm diagnosis through end of study period.
- Controls for the multivariable risk factor analysis, a random sample of matched patients without myocarditis will be selected, e.g. with an encounter date during the same month as the index date for the myocarditis case, and with a similar amount of follow-up time from entry into the cohort and activity in the database. Additional matching criteria may be

determined, and details of the matching methods and appropriate modeling considerations will be provided in the statistical analysis plan (SAP).

**Variables:** The outcome in this study is myocarditis, categorized into three cohorts: 1) myocarditis post mRNA COVID-19 vaccination, 2) myocarditis post-SARS-CoV-2 infection, or 3) acute/viral myocarditis pre-2020. Myocarditis will be identified with ICD-10-CM codes in EHR and claims data. In addition, Brighton Collaboration Criteria will be used as the basis during manual reviews of electronic medical notes by two clinicians at Optum to validate a subset of the cases. Exposure variables will include potential risk factors for myocarditis including demographic characteristics, diagnoses and procedures defined with ICD-10 codes, treatments (prescriptions) and laboratory tests identified in the EHR. Covariates include medical comorbidities and other treatments at index, as well as healthcare utilization before index, and may include other factors not considered as risk factors for myocarditis.

**Data sources:** Optum's statistically de-identified Electronic Health Record (EHR) and Integrated Claims-Clinical dataset, which combines adjudicated claims data (where available) with Optum's EHR data, are the data sources for this study. In addition, this study will use data available in the medical records for a subset of myocarditis patients that have clinical patient notes and other data that cannot be mapped into the larger structured database.

**Study size:** Optum's longitudinal EHR repository is derived from dozens of healthcare provider organizations in the US, that include more than 57 contributing sources and 111K sites of care: treating more than 106 million patients receiving care in the US. Based on initial feasibility assessment of the Optum EHR database, there were approximately 240 myocarditis cases within 21 days of mRNA vaccination, 1,730 myocarditis cases after SARS-CoV-2 infection, and 7,200 myocarditis cases prior to 01 November 2019. In addition, the large size of the database will allow for matching of each myocarditis case with controls for the risk factor analyses.

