# **Myocarditis cases:**

- 2. Diagnosis of myocarditis identified using ICD codes in EHR and/or claims when available. (ICD codes will be provided in the SAP)
- 3. At least one myocarditis inpatient record or two myocarditis records of any type dated greater than or equal to 30 days apart
- 4. Myocarditis diagnosis date between 01 January 2016 most recent EHR data available (31 March 2023)
- 5. At least 365 days of enrollment or activity in the EHR prior to the index myocarditis diagnosis.

Myocarditis cases meeting the above criteria will be divided into the following three cohorts with their own unique inclusion criteria:

- a) Cohort 1 Post- mRNA COVID-19 vaccine myocarditis cases:
  - 1. Myocarditis diagnosis date 11 December 2020 or later
  - 2. Record of mRNA vaccination within 21 days prior to the myocarditis diagnosis without a record of SARS-CoV-2 positive test within 8 weeks prior to myocarditis diagnosis
  - 3. Availability of medical notes to use for confirmation of myocarditis post-mRNA COVID-19 vaccination thirty days before or after the index event
- b) Cohort 2 Post- SARS-CoV-2 infection myocarditis cases:
  - 1. Myocarditis diagnosis date 01 January 2020 or later
  - 2. Record of SARS-CoV-2 positive test within 8 weeks prior to myocarditis diagnosis, with no record of mRNA COVID-19 vaccination during that time
  - 3. Availability of medical notes to use for confirmation of myocarditis post-SARS-CoV-2 infection thirty days before or after the index event
- c) Cohort 3 Pre-COVID-19-era acute/viral myocarditis cases:
  - 1. Most recent Myocarditis diagnosis date prior to 01 November 2019
  - 2. Availability of medical notes to use for confirmation of myocarditis within thirty days before or after the index event

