For the validation process using the electronic clinical notes (which will be converted to deidentified structured data for analyses), the Optum Natural Language Programming (NLP) team will determine if clinical notes are available for all qualifying patients with post-vaccine myocarditis, all qualifying post-SARS-CoV-2 infection myocarditis, as well as random samples of myocarditis diagnosed pre-2020. Optum will perform a series of "enhanced search" queries on the patient notes to determine key term content. Next, the Optum NLP team will use the key terms to extract note snippets into a file for review by the Optum Clinical team. These notes snippets will then be used to validate myocarditis cases per the Brighton Collaboration Criteria that were identified in the EHR using the inclusion and exclusion criteria specified in Section 9.2. After clinical review of the notes involving two clinicians from Optum, and categorization of the content for analysis, the resulting table of criteria will be created. The myocarditis cases will then be classified as validated or not validated, and relevant information entered into a spreadsheet that will serve as the data collection tool. Finally, the Optum clinical review team will provide these results of the case validation to the Optum Health Economics and Outcomes Research (HEOR) analytics team, whose members will identify matched controls for each case and conduct the multivariable analyses to assess risk factors for myocarditis

 CFR 164.514(b)(1).

 Guidance Regarding Methods for De-identification of Protected Health Information in Accordance with the Health Information Insurance Portability and Accountability Act (HIPAA) Privacy Rule (Dated as 04 September 2012, as first released on 26 November 2012).

using the structured data. This information will also be used to calculate the PPV of the algorithm used to initially identify the myocarditis cases in the structured EHR database.

Data will be transferred from the clinical review team to Optum's HEOR team via standard Data Transfer API (application programming interface). Extraction, merging, and cleaning of EHR and NLP-rendered data will be performed and adjudicated by at least two HEOR programmers and two HEOR analysts/directors. All data steps and code locations are formally documented in a data dictionary and are reviewed by the directing analyst and researcher before commencement of programming.

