myocarditis. Laboratory results and vital signs/other biometric measures may be incomplete and therefore only available for a subset of the patients. Another limitation inherent to EHR databases is that information on prescriptions recorded for outpatients in this database does not necessarily indicate that the medication was consumed or taken as prescribed; similarly, medications filled over the counter or provided as samples by the physician may not be recorded in the database. Vaccine administrations or SARS-CoV-2 infections may not be recorded in the EHR, and so myocarditis after vaccination or COVID-19 infection may be missed. Similarly, due to the nature of EHR data, conditions not requiring treatment or office visits tend to be systematically under-recorded; therefore, it is possible that this study may only capture severe conditions that are considered in the risk factor models. Patients may have received health care outside of the network of providers and healthcare organizations that contribute to the Optum databases, or prior to having the index diagnosis and we may not be able to exclude the possibility that a patient was diagnosed with myocarditis, as well as other risk factors, prior to entry into a healthcare system where Optum has EHR access. Furthermore, if observed results using ICD-9 codes significantly differ from observed results using ICD-10 codes as a result of Centers for Medicare & Medicaid Services (CMS) and the National Center for Health Statistics (NCHS) ICD-9 to ICD-10 transition, we may modify our definitions as necessary.

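### Notes dated only before the index diagnosis satisfy the notes criterion in every cohort, and review has only two outcomes, so cases whose notes miss the episode count as false positives and PPV may be understated

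*Protocol*

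**What the plan says.** The Abstract (Population) and Section 9.1 define each cohort with a notes window on either side of index; the Abstract wording is "allowing for at least 30 days pre or post index for medical notes to" confirm the diagnosis. Section 9.2.1 repeats this as an inclusion criterion:

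- Cohort 1: "Availability of medical notes to use for confirmation of myocarditis post-mRNA COVID-19 vaccination thirty days before or after the index event"
- Cohort 2: "Availability of medical notes to use for confirmation of myocarditis post-SARS-CoV-2 infection thirty days before or after the index event"
- Cohort 3: "Availability of medical notes to use for confirmation of myocarditis within thirty days before or after the index event"

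No cohort needs a note on or after the index date or from the index encounter, and no minimum number of notes is set. The qualifying code may come from the EHR or from claims (9.2.1). Notes exist for only a subset of patients (9.2) and come from only some EHR systems (9.6).

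Section 9.6 describes a key-term search, extraction of snippets and review by two clinicians, after which "The myocarditis cases will then be classified as validated or not validated". The result feeds the PPV of the case algorithm, which secondary objective 2 compares across cohorts. Section 9.7 also reruns the risk-factor models on the validated cases.

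**The concern.** A PPV from record review is interpretable only if the records reviewed could have shown the event. Here a patient can be coded in claims or at one site and hold notes only from another, earlier contact. Section 9.9 accepts that such fragmentation occurs: "Patients may have received health care outside of the network of providers and healthcare organizations that contribute to the Optum databases". The clinicians would find nothing about the episode, and the only class left for that patient is not validated. Missing evidence is then counted as evidence against the diagnosis.

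Two results are exposed. The PPV of the code definition would be too low, and any difference between cohorts in how often notes miss the episode would appear as a difference in coding validity. True cases would also drop out of the validated-case models. That matters most in Cohort 1, the smallest cohort, with about 240 cases in the feasibility count.

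**Working it through.** The protocol states no PPV, precision target or sample size for the validation, so there is no planned figure to reproduce. The check has two parts.

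**1. Windows (Section 9.2.1)**

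- Cohort 1 requires a "Record of mRNA vaccination within 21 days prior to the myocarditis diagnosis". A lag of 0 to 21 days always lies inside a 30-day pre-index window.
- Cohort 2 requires a "record of SARS-CoV-2 positive test within 8 weeks prior to myocarditis diagnosis", a lag of 0 to 56 days. Only lags of 0 to 30 days fall inside the window: 31 of 57 possible values, or 54% if lags were uniform (an assumption).
- Cohort 3 has no defining contact before index, but any visit in the preceding 30 days can supply a pre-index note.

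**2. Effect on PPV**

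Let P be the true PPV and f the share of reviewed cases whose notes do not cover the episode. Suppose all of these are classed not validated, review is otherwise correct, and P is the same with and without coverage. Then

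observed PPV = P × (1 − f).

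Both P and f are assumed, so a range is shown:

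| P | f = 5% | f = 10% | f = 20% | f = 30% |
|---|---|---|---|---|
| 0.60 | 0.57 | 0.54 | 0.48 | 0.42 |
| 0.80 | 0.76 | 0.72 | 0.64 | 0.56 |
| 0.90 | 0.855 | 0.81 | 0.72 | 0.63 |

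Of the 240 Cohort 1 cases in Section 9.5, f of 5%, 10% or 20% is 12, 24 or 48 patients.

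For scale, the 95% half-width is 1.96 × √[P(1 − P)/n]. At P = 0.80 it is 1.96 × √(0.16/240) = 5.1 points for Cohort 1 and 1.96 × √(0.16/1,730) = 1.9 points for Cohort 2. The loss at f = 10% is 0.80 − 0.72 = 8 points, larger than either.

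**3. Difference between cohorts**

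With P = 0.80 in both, Cohort 1 minus Cohort 3 is 0.80 × (f₃ − f₁):

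- f₁ = 10%, f₃ = 0%: −8.0 points
- f₁ = 10%, f₃ = 5%: −4.0 points
- f₁ = 10%, f₃ = 10%: 0
- f₁ = 5%, f₃ = 10%: +4.0 points

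If the true PPVs differ, the order can also hold against the bias: 0.80 × 0.90 = 0.720 in Cohort 1 against 0.70 × 0.98 = 0.686 in Cohort 3. The sign rests entirely on quantities the protocol does not give.

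**The case against.** The strongest reply is that the rule is identical in all three cohorts and that its wording, notes to be used for confirming myocarditis, implies relevant notes. Only snippets containing key terms reach the clinicians, so a patient with an irrelevant visit note might never enter review. Each case also needs an inpatient myocarditis record or two records at least 30 days apart, which makes a complete absence of episode notes less likely. Symptoms and work-up can precede the first code, so pre-index notes are not always empty. Finally, operational detail is left to the SAP, and the models are also run on all code-identified cases.

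Much of this stands as a limit on size. It does not remove the defect. The phrase about confirmation carries no content requirement. The record-count rule concerns codes, not notes. The protocol does not say what happens to a case whose search yields no snippet about the episode. The SAP may refine the handling, but the either-side criterion and the two-class outcome are fixed in the protocol itself.

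A reader might go further and infer that vaccination and test visits supply these notes, so that PPV in Cohorts 1 and 2 is pushed below that in Cohort 3. The document does not support this. It requires a record of vaccination or of a positive test, and Section 9.4 lists immunizations and laboratory results as structured data elements; nowhere does it say that such contacts leave a clinical note. In Cohort 2 a test at a lag of 31 to 56 days lies outside the window. Cohort 3 is indexed on its most recent code, and Section 9.9 warns that codes may record a historical event, which could lower that cohort's own PPV.

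**Conclusion.** The concern holds in a non-directional form. In every cohort, pre-index notes alone can admit a case to validation, and with only two review outcomes an undocumented episode counts against the code definition. PPV may therefore be understated, by a factor of (1 − f) under the assumptions above. The value of f is unknown; at 10% and a true PPV of 80% the loss would be 8 points, enough to matter against the precision available in Cohort 1.

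The loss may differ by cohort. A larger one in Cohort 1 is most plausible because its vaccination contact always falls within the pre-index window, but this depends on such contacts producing notes. Neither the existence nor the sign of a gap relative to Cohort 3 can be established from the protocol. The reach is secondary objective 2 and the validated-case models; the models on all code-identified cases are unaffected by the review classification.

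**What to change.** In Sections 9.1, 9.2.1 and 9.6, and in the matching Abstract text:

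1. Compute the main PPV in each cohort among cases with at least one note from the index encounter or dated from index to 30 days after it. Keep earlier notes as supporting evidence. This still admits notes written during an admission before the code was posted.
2. Add a third review outcome, not assessable, for cases whose notes do not document the episode. Keep not validated for cases where the episode is documented and the Brighton criteria are not met. This also handles unrelated notes dated after index, which a date rule alone would let through.
3. Report the number not assessable, and the number without a qualifying note, by cohort.
4. Give the PPV on all reviewed cases alongside, so the effect of the rule is visible.
5. Align the window wording: the Abstract and 9.1 speak of at least 30 days, 9.2.1 of thirty days or within thirty days.

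The date rule should define the PPV denominator and not exclude patients from the study. As an exclusion it could drop cases whose work-up preceded the code, notably in Cohort 3 with its most-recent index.

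The cost is a few wording changes, one date filter on notes already held and one extra category on the review form. The downside is a somewhat smaller PPV denominator, chiefly in Cohort 1. The change does not return unassessable true cases to the validated-case models; it shows only how many were lost.

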# Primary objective:

1. To assess and compare demographic, medical history, and comorbidities that may be risk factors for myocarditis in each of three cohorts: 1) Myocarditis after mRNA COVID-19 vaccine, 2) Myocarditis after SARS-CoV-2 infection (2020-2022), or 3) Acute/viral myocarditis prior to the COVID-19 era (pre-2020).

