- Controls risk-set matched on e.g. month/year of cohort entry, duration of follow up (from cohort entry), integrated delivery network (IDN). Matching criteria will be detailed in the SAP.
- Timeframe for each myocarditis sub-cohort:
  - 1) Post-vaccination myocarditis: December 11, 2020 November 01, 2022
  - 2) Post-SARS-CoV-2 myocarditis: January 01, 2020 November 01, 2022
  - 3) Pre-COVID era myocarditis: January 01, 2016 November 01, 2019

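### Cohort 2 opens 345 days before Cohort 1, and the time-period stratifier that could make their comparison concurrent is missing from the analysis section

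*Protocol*

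**What the plan says.** The two COVID-era cohorts open on different dates everywhere the protocol defines them.

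- Section 4 (Abstract, Population): Cohort 1 is the first "myocarditis diagnosis code within 21 days after vaccination from 11 December 2020 to most" recent data. Cohort 2 is the first diagnosis "code within 8 weeks after a positive SARS-Cov-2 test from 01 January 2020 to most recent" data. Section 9.1 gives the same start dates.
- Section 9.2.1: "Myocarditis diagnosis date 11 December 2020 or later" for Cohort 1, and "Myocarditis diagnosis date 01 January 2020 or later" for Cohort 2.
- Section 9.1, notes to Figure 1: "Post-vaccination myocarditis: December 11, 2020 November 01, 2022", and "Post-SARS-CoV-2 myocarditis: January 01, 2020 November 01, 2022". These notes close both windows on 01 November 2022, whereas Section 9.2.1 lets diagnoses run to 31 March 2023.

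The primary objective (Sections 4 and 8) is "To assess and compare demographic, medical history, and comorbidities that may be risk factors for myocarditis in each of three cohorts". Section 7 adds the aim of putting post-vaccination myocarditis in a broader context.

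On calendar time, Section 9.2.1 requires each control to have an encounter in the same month as its own case. Secondary objective 1 (Sections 4 and 8) lists time period among the stratifiers to be applied within each cohort. The subgroup lists meant to carry out the secondary analyses, in the abstract and in Section 9.7, name case definition, age group, sex and follow-up time. They do not name time period. The limitations in Section 9.9 do not mention the differing windows.

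**The concern.** Cohort 3 closes on 01 November 2019, so Cohort 2 is the only COVID-era group against which Cohort 1 can be read. Cohort 2 cases diagnosed before 11 December 2020 arose before the protocol's own vaccination window opened, so no Cohort 1 case could have arisen beside them. Later Cohort 2 cases did arise in that window. They may even have been vaccinated earlier, because Section 9.2.1 bars mRNA vaccination only in the 8 weeks before diagnosis. Cohort 2 therefore pools two periods, and only one has a possible Cohort 1 counterpart.

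Some variables in Table 1 depend on the calendar by construction, for example prior COVID-related treatment. If the early and late Cohort 2 cases differ on such a variable, a side-by-side table of Cohort 1 and Cohort 2 shows a difference that belongs partly to the period. A reader would naturally assign it to the trigger, vaccine or infection. The same can happen when the two cohorts' odds ratios for one risk factor are set beside each other.

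**Working it through.** The protocol states no sample size, power or alpha for this comparison (Section 9.5), so there is no figure of the plan's own to reproduce. The check has four steps.

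**1. Non-concurrent time.** Inputs: start dates from Section 9.2.1, end dates from the Figure 1 notes (01 November 2022) and Section 9.2.1 (31 March 2023).

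- 01 January to 10 December 2020 = 345 days.
- Cohort 2 window to 01 November 2022 = 1,036 days; 345 / 1,036 = 33.3%. Shared window: 1,036 − 345 = 691 days.
- Cohort 2 window to 31 March 2023 = 1,186 days; 345 / 1,186 = 29.1%. Shared window: 1,186 − 345 = 841 days.

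**2. Cases affected.** Section 9.5 gives about 1,730 Cohort 2 cases but not their spread over time. Assuming uniform accrual, 1,730 × 345 / 1,186 = 503 and 1,730 × 345 / 1,036 = 576. Over an assumed early share of 10% to 50%, the count runs from 173 to 865.

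**3. Possible distortion (illustration; all prevalences assumed).** Let a characteristic have prevalence p in Cohort 1 and in late Cohort 2, and q in early Cohort 2, with early share s. Pooled Cohort 2 prevalence = s·q + (1 − s)·p. The concurrent odds ratio is 1.00 by construction.

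| p | q | s | Pooled Cohort 2 | Difference from Cohort 1 |
|---|---|---|---|---|
| 20% | 30% | 10% | 21.0% | 1.0 point |
| 20% | 30% | 29% | 22.9% | 2.9 points |
| 20% | 30% | 33.3% | 23.3% | 3.3 points |
| 20% | 30% | 50% | 25.0% | 5.0 points |
| 25% | 40% | 15% | 27.25% | 2.25 points (OR 1.12) |
| 25% | 40% | 29% | 29.35% | 4.35 points (OR 1.25) |
| 25% | 40% | 50% | 32.5% | 7.5 points (OR 1.44) |

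For example, the last OR is (0.325 / 0.675) / (0.25 / 0.75) = 1.44. If q equals p, the distortion is nil.

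**4. Precision cost of a concurrent comparison.** With about 240 Cohort 1 cases (Section 9.5) and n₂ Cohort 2 cases kept, the SE ratio = √[(1/240 + 1/n₂) / (1/240 + 1/1,730)].

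- n₂ = 1,227 (1,730 − 503): 1.025
- n₂ = 1,154 (1,730 − 576): 1.030
- n₂ = 865 (half early): 1.059

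The loss is small because Cohort 1 limits precision.

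**The case against.** The strongest reply has four parts.

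*The odds ratios are already aligned on calendar time.* Each control shares its case's month, and the Figure 1 notes describe risk-set matching. This stands for each cohort's own models. A reader might infer from the differing windows that the Cohort 2 odds ratios are confounded by period, or that opening the cohort in January 2020 is an error. The documents support neither. The early cases are valid for the within-cohort analysis. What matching cannot do is line up Cohort 1 cases with Cohort 2 cases, or keep the odds ratios themselves from varying by period.

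*The protocol does consider time period.* Secondary objective 1 names it, so it would be wrong to say that the plan ignores calendar time. But the stratifier is secondary, works within cohort, and is absent from both lists that should implement it.

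*The SAP will settle the form of the comparison.* Section 9.7 leaves detailed methodology to the SAP and specifies no formal Cohort 1 versus Cohort 2 test. This limits the point to interpretation of side-by-side results. It does not remove it, because the windows, the comparative objective and the mismatch between objective and subgroup list are all fixed in the protocol.

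*The whole of 2020 to 2022 is the stated target, and eras differ by design.* The primary objective does define Cohort 2 that way, so the full-window comparison is legitimate and should stay. Cohort 3 shares no calendar time with either of the other cohorts, and no date restriction can change that. Neither fact is a reason to omit a concurrent view where one is available.

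**Conclusion.** The point holds as a cheap improvement to how one comparison is presented. The 345-day gap and its 29% to 33% share of the Cohort 2 window follow directly from the stated dates. As written, the plan cannot separate trigger from calendar period when Cohort 1 is set beside Cohort 2, because the only stratifier that could help is dropped between secondary objective 1 and Section 9.7.

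The size of any distortion is not known. The 29% to 33% is a share of days; reading it as a share of cases assumes uniform accrual, which the documents do not state. The 1 to 7.5 point differences and the odds ratios of 1.12 to 1.44 rest on assumed prevalences. A reader might also infer that early Cohort 2 cases differed in access to testing or in treatment. The protocol does not say so. The dates show only that these cases precede its vaccination window. The case for the change rests on the design allowing such a difference to be misread, at little cost to prevent.

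**What to change.** 1. Add time period to the subgroup lists in Section 9.7 and the abstract, with a cut at 11 December 2020, so that they match secondary objective 1.
2. State in both places that the Cohort 1 versus Cohort 2 comparison, of case characteristics and of odds ratios, is also presented using only Cohort 2 cases with index dates from 11 December 2020 and their matched controls, beside the full-window comparison.
3. State that a difference seen only in the full window will not be attributed to the trigger.
4. Keep the full Cohort 2 from 01 January 2020 for its own case-control models.

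Quarterly stratification or weighting should not be required. The shared window of 691 to 841 days spans roughly eight to nine quarters, so about 240 Cohort 1 cases, if spread evenly, would leave only 27 to 30 per quarter (240 / 9 and 240 / 8). The standard-error figures above cover the date restriction alone.

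The cost is a short text change, one date filter and one extra analysis. Standard errors for that comparison would be about 2% to 3% wider, or about 6% if half of Cohort 2 is early. The report will carry two versions of the comparison, which is why item 3 is needed. Comparisons with Cohort 3 remain non-concurrent and are not repaired by this change.
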